d=does not need to be repeated if HbA1c is available from within the prior 3 months. If not available, can be performed within 3 weeks after randomization.

429 **1.4 General Considerations**

The study is being conducted in compliance with the policies described in the DRCR.net Policies
document, with the ethical principles that have their origin in the Declaration of Helsinki, with
the protocol described herein, and with the standards of Good Clinical Practice.

- 434 The DRCR.net Procedures Manuals (Visual Acuity-Refraction Testing Procedures Manual, OCT
- 435 Manuals, and Study Procedures Manual) provide details of the examination procedures and
- 436 intravitreal injection procedure.
- 437
- 438 Data will be directly collected in electronic case report forms, which will be considered the 439 source data.
- 440

441 The participant will be masked to the treatment group assignment. Visual acuity testers

- 442 (including refractionists) and OCT technicians will be masked to treatment group at the primary
- 443 outcome visit (24 weeks). Investigators will not be masked to treatment group assignment.
- 444
- There is no restriction on the number of study participants to be enrolled by a site.
- 446
- 447 A risk-based monitoring approach will be followed, consistent with the FDA "Guidance for

448 Industry Oversight of Clinical Investigations — A Risk-Based Approach to Monitoring" (August

- 449 2013).
- 450
- 451 The risk level is considered to be research involving greater than minimal risk.

452	
453 454	Chapter 2. STUDY PARTICIPANT ELIGIBILITY AND ENROLLMENT
454	STUDI FARTICIFANT ELIGIDILITT AND ENROLLMENT
456	2.1 Identifying Eligible Study Participants and Obtaining Informed Consent
457	A minimum of 150 eyes are expected to be enrolled into the randomization phase. Assuming that
458	20% of the study participants have two study eyes, this equates with an enrollment of about 125
459	study participants, with a goal to enroll an appropriate representation of minorities. As the
460	enrollment goal approaches, sites will be notified of the end date for recruitment. Study
461	participants who have signed an informed consent form or are in the run-in phase can be
462	randomized up until the end date, which means the recruitment goal might be exceeded.
463	1 7 8 8
464	Potential eligibility will be assessed as part of a routine-care examination. Prior to completing

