814 The treatment groups are as follows: 815 Group A: Sham + intravitreal ranibizumab 0.3 mg • Group B: Intravitreal dexamethasone +intravitreal ranibizumab 0.3 mg 816 • For both treatment groups, the initial ranibizumab injection must be given on the day of 817 818 randomization. The sham or dexamethasone injection will be given within 0-8 days of the 819 ranibizumab injection. If the injections are given consecutively on the same day, the sham 820 injection must be given first in Group A and the ranibizumab injection must be given first in 821 Group B. 822 823 Focal/grid laser is not permitted in the study eye. 824 825 4.6 Follow-Up Study Visits During the Randomization Phase The schedule of protocol-specified follow-up visits post-randomization is as follows: 826 827 828 • 4 weeks (± 1 week) 829 • 8 weeks (± 1 week) 830 • 12 weeks (± 1 week) 831 • 16 weeks (± 1 week) 832 • 20 weeks (± 1 week) 833 • 24 weeks (±1 week)– primary outcome visit 834 835 A minimum of 21 days is required between injections. An additional visit may be required for 836 completion of the second (steroid/sham) injection at randomization and 12 weeks. 837 838 4.7 Follow-Up Testing Procedures During the Randomization Phase 839 The following procedures will be performed at each protocol visit unless otherwise specified. A 840 grid in section 1.3 (J) summarizes the testing performed at each visit. 841 842 Visual acuity testers (including refractionist) and OCT technicians will be masked to treatment 843 group at the primary outcome visit (24 weeks). 844 845 1. Best-corrected E- ETDRS visual acuity testing in each eye A protocol refraction in the study eye is required at all protocol visits. Protocol refraction 846 • 847 in the non-study eye at the 24 week-visit only. When a refraction is not performed, the 848 most-recently performed refraction is used for the testing. 849 2. OCT on the study eye 850 3. Ocular exam on the study eye, including slit lamp examination, lens assessment, 851 measurement of intraocular pressure and dilated ophthalmoscopy 852 853 All of the testing procedures do not need to be performed on the same day, provided that they are 854 completed within the time window of a visit and prior to initiating any retreatment. 855 856 Testing procedures at unscheduled visits are at investigator discretion. However, it is 857 recommended that procedures that are performed should follow the standard DRCR.net protocol 858 for each procedure. If the study participant returns following a protocol visit specifically to 859 receive a study injection, testing prior to the injection is at investigator discretion. 860

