- Report the observed No. (%) by treatment group, adjusted difference in proportions, 95% confidence interval, and *P*value from treatment group comparisons
- AUC outcome: Mimic the linear mixed effect model in the primary analysis limiting the cohort to 24-week completers. No imputation will be performed.
 - Report mean ± SD and median [IQR] by treatment group, adjusted mean difference, 95% confidence interval, and *P*-value from treatment group comparison.
- 6. Summarize safety events occurred at any time during randomization phase
 - a. Ocular adverse events [eTable 5]
 - i. Tabulate No. (%) of eyes experienced at least one event by treatment group using *eyesRand* dataset
 - At least one ocular adverse events in the study eye
 - Increased intraocular pressure (IOP) events (a composite outcome, defined as any of the below). Each component will also be reported separately.
 - IOP increased \geq 10 mmHg from randomization at any visit
 - \circ IOP \geq 30 mmHg at any visit
 - Received ocular anti-hypertensives
 - Endophthalmitis
 - Inflammation
 - Any retinal detachment (a composite outcome, defined as any of the below). Each component will also be reported separately.
 - Traction retinal detachment
 - Rhegmatogenous retinal detachment
 - Unspecified retinal detachment
 - Retinal tears

- Retinal hemorrhage
- Vitreous hemorrhage
- Cataract extractions
- Glaucoma surgery
- Received post-injection treatment to lower IOP
- Migration of dexamethasone implant to the anterior chamber and subsequent corneal complications (combination group only)
 - Note: There is no specific MedDRA term for this type of adverse event. Instead, perform a manual check by searching for keywords "migration" and "anterior chamber" in the description field on the AE form, limiting to records in randomized eyes at post randomization.
- ii. Compare the frequency between treatment groups using Fisher's exact test and report *P*-value.
- iii. Footnote No. of patients experienced multiple types of ocular adverse events as listed above (if any)
- b. Systemic adverse events
 - i. All systemic adverse events will be reported by treatment group: combination group (unilateral participants), ranibizumab group (unilateral participants), and bilateral participants.
 - ii. Reduce *eyesRand* dataset to patient-level as a temporary dataset *ptRand*
 - iii. Tabulate No. (%) of participants experienced at least one event [eTable 6]
 - At least one systemic adverse event

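### IOP events count at any visit, and unmasked investigators decide on the extra readings, so unequal measurement can affect the arm comparison; the size is unknown and probably modest

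*SAP*

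**What the plan says.** **Counting rule.** SAP item 6 opens with "Summarize safety events occurred at any time during randomization phase". Under 6.a.i, the increased-IOP composite has three components, each also reported separately: a rise of at least "10 mmHg from randomization at any visit", a value of at least "30 mmHg at any visit", and receipt of ocular anti-hypertensives. Item 6.a.ii reads "Compare the frequency between treatment groups using" and names Fisher's exact test. The unit is the eye with at least one event. The supplied text does not define a visit for this purpose and does not account for the number of readings.

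**Measurement rule.** Protocol 4.6 and 4.7 require IOP at weeks 4, 8, 12, 16, 20 and 24 in both arms. Section 4.6 allows an additional visit for the steroid or sham injection at randomization and at week 12. For a return visit made to receive an injection, section 4.7 says "testing prior to the injection is at investigator discretion". It also says "Testing procedures at unscheduled visits are at investigator discretion".

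**Masking.** Protocol 1.4: "Investigators will not be masked to treatment group assignment". Participants are masked, and visual acuity testers, refractionists and OCT technicians are masked at week 24. No masking is stated for whoever measures IOP.

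**The concern.** For an outcome defined as at least one exceedance, each further reading can add an event and none can remove one. Here the further readings are chosen by someone who knows the arm. Protocol 6.5.1.2 describes sizeable pressure rises after the implant, so an investigator has more reason to check pressure in a steroid eye than in a sham eye. If that happens, the difference in eTable 5 mixes the drug effect with measurement frequency.

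Raised IOP is a named main safety outcome (protocol 1.3 I and 7.5), and assessing safety is a stated objective (1.2). Unequal measurement of this kind would overstate the steroid harm, and the planned table would not let a reader separate the two sources.

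**Working it through.** The documents give no expected IOP difference, no power for IOP and no number of extra readings, so there is no planned figure to reproduce. What follows is a range under stated assumptions.

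**Inputs from the documents**
- Scheduled post-randomization readings per eye: 6 in both arms (protocol 4.6, 4.7).
- Randomized eyes per arm: 75 (protocol 7.1, 7.2).
- Rise of 10 mmHg or more after a first implant in the cited vein-occlusion studies: 12.6% (protocol 6.5.1.2).

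**Assumptions**
- k extra readings in every steroid eye and none in control eyes. This is the extreme imbalance for a given k.
- Chance exceedance per reading q = 0.5%, 1% or 2%, no drug effect, readings independent.

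**Check 1: false excess with no drug effect.** Control risk = 1 − (1 − q)^6; steroid risk = 1 − (1 − q)^(6 + k). The last column is the exact probability, with 75 eyes per arm, that Fisher's test gives P<0.05 with the steroid arm worse.

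| q | k | Control | Steroid | Difference (points) | Steroid worse, P<0.05 |
|---|---|---|---|---|---|
| 0.5% | 0 | 3.0% | 3.0% | 0 | 0.3% |
| 0.5% | 1 | 3.0% | 3.4% | 0.5 | 0.6% |
| 0.5% | 2 | 3.0% | 3.9% | 1.0 | 1.0% |
| 0.5% | 4 | 3.0% | 4.9% | 1.9 | 2.5% |
| 1% | 0 | 5.9% | 5.9% | 0 | 0.9% |
| 1% | 1 | 5.9% | 6.8% | 0.9 | 1.7% |
| 1% | 2 | 5.9% | 7.7% | 1.9 | 3.0% |
| 1% | 4 | 5.9% | 9.6% | 3.7 | 7.5% |
| 2% | 0 | 11.4% | 11.4% | 0 | 1.4% |
| 2% | 1 | 11.4% | 13.2% | 1.8 | 3.2% |
| 2% | 2 | 11.4% | 14.9% | 3.5 | 6.0% |
| 2% | 4 | 11.4% | 18.3% | 6.9 | 15.8% |

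Example: q = 1%, k = 2 gives 1 − 0.99^6 = 5.9% and 1 − 0.99^8 = 7.7%. For k = 1 or 2 the excess is 0.5 to 3.5 points, which is 75 × 0.0049 = 0.4 to 75 × 0.0351 = 2.6 eyes. The k = 0 rows are what a count restricted to protocol visits would give: no difference.

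**Check 2: inflation of a real event rate.** Take a six-reading risk of 12.6% or 25% in the steroid arm and an exchangeable Gaussian model with within-eye correlation 0 to 0.7. The 25% is an assumed upper value. The nearby 25.5% in protocol 6.5.1.2 is the share of eyes started on IOP-lowering medication, not a threshold rate.
- One extra reading: 12.6% becomes 13.6% to 14.5%; 25% becomes 26.6% to 28.5%. Relative rise 6% to 15%.
- Two extra readings: 12.6% becomes 14.5% to 16.4%; 25% becomes 27.9% to 31.9%. Relative rise 12% to 31%.

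**Check 3: what the injection-only visits can contribute.** When the injections fall on different days, ranibizumab comes first and the implant or sham follows within 8 days (protocol 4.5, 4.8). Testing at the return visit is before that injection.
- At randomization the steroid eye has no study implant yet, so the reading cannot show an effect of it.
- At week 12 the reading comes within 8 days of the week-12 ranibizumab injection, so it largely repeats the week-12 protocol reading.

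The two visits together therefore carry less than two full extra readings. The number of readings at unscheduled visits is unknown.

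**The case against.** The strongest reply is that measurement is mostly balanced by design. Six readings are mandatory in both arms. Injection-only visits arise for steroid and sham alike, under the same 0 to 8 day rule. In participants with two study eyes, one eye is in each arm and visits are shared. An eye counts once, so a reading after an event has been recorded changes nothing. All of this stands, and it is why the effect is probably modest. It does not remove the point, because the choice to measure at a discretionary visit is still made with knowledge of the arm.

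Second, the SAP does not define a visit here. The supplied document is a technical plan that points to a separate protocol SAP, and protocol 7.5 defers event definitions to the detailed plan, so discretionary readings might be excluded there. That stands as an uncertainty. The plain wording includes them, and a clear definition is needed either way.

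Third, SAP item 3.d reports by arm how often the steroid or sham injection was given on the same day as ranibizumab. This shows how often an extra injection visit was needed, but not whether IOP was measured there, nor anything about unscheduled visits.

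Fourth, dropping discretionary readings from the tested outcome could hide real harm: a spike found and treated between visits may be normal at the next protocol visit. This stands, and it is why the any-visit test should be kept and not replaced.

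**Conclusion.** The any-visit rule, combined with unmasked discretion over extra readings, leaves the between-arm IOP comparison open to unequal measurement, and nothing in the supplied text corrects for it or shows its extent. The direction would be to overstate steroid harm.

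A reader might infer more: that the comparison is biased, or that steroid-arm events are inflated by 12% to 31%. The documents do not support either. The 12% to 31% needs two full extra readings in every steroid eye and none in control eyes, and the documents neither give nor imply that. One fully one-sided extra reading gives 6% to 15%, and the timing of the injection-only visits makes even that generous for those visits. Under no drug effect, one or two one-sided extra readings give a false steroid-worse result with probability 0.6% to 6.0%. Only many one-sided readings would matter much (2.5% to 15.8% with four). All these figures rest on assumed values of k, q and the within-eye correlation.

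This is a cheap improvement to a safety table, not a flaw that undermines it.

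**What to change.** In SAP item 6.a.i:

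1. State which visits the any-visit rule covers. Keep those rows and their Fisher test as the full safety tabulation.
2. Add a row for each threshold (rise of at least 10 mmHg; value of at least 30 mmHg) computed only from the six protocol visits, weeks 4 to 24, in both arms, with the same between-group comparison.
3. Show the number of post-randomization IOP readings per eye by arm.
4. Footnote the composite: receipt of ocular anti-hypertensives also depends on unmasked decisions, since protocol 5.6 leaves treatment of raised IOP to the investigator. The added rows do not correct that component.

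**Cost.** A few lines of SAP text and a few rows in eTable 5, with no change to visits or clinical procedures. The protocol-visit readings are already collected; the count in item 3 needs discretionary readings to have been recorded. The downside is that a spike seen only between protocol visits is absent from the added rows, though it stays in the any-visit rows.

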- 311 addition of steroid to an anti-VEGF treatment regimen in eyes that have persistent DME despite

312	anti-VEGF treatment increases visual acuity and decreases DME in the short term, compared
313 314	with continued anti-VEGF treatment alone.
314 315	1.2 Study Objectives
315	1.2 Study Objectives To assess the short-term effects of combination steroid+anti-VEGF therapy on visual acuity and
317	retinal thickness on OCT in comparison with that of continued anti-VEGF therapy alone in eyes
318	with persistent central-involved DME and visual acuity impairment despite previous anti-VEGF
319	treatment.
320	
321	Furthermore, this phase II study is being conducted (1) to determine whether the conduct of a
322	phase III trial has merit based on functional and anatomic outcomes, (2) to estimate recruitment
323	potential of a phase III investigation, (3) to provide information needed to design a phase III trial,
324	and (4) to assess the safety of administering combination steroid+anti-VEGF therapy in eyes
325	with persistent DME. The study is not designed to definitively establish the efficacy of
326	corticosteroid+anti-VEGF therapy in the treatment of persistent central-involved DME.
327	
328	1.3 Study Design and Synopsis of Protocol
329	
330	A. Study Design
331	
332	• Randomized, controlled phase II multi-center clinical trial
333	
334	B. Major Eligibility Criteria
335	
336	• Age ≥ 18 years
337	• Type 1 or type 2 diabetes
338	• The study eye must meet the following criteria:
339	> Visual acuity letter score in study eye ≤ 78 and ≥ 24 (approximate Snellen
340	equivalent 20/32 to 20/320)
341	Ophthalmoscopic evidence of center-involved DME
342	OCT CSF thickness value (microns):
343	■ Zeiss Cirrus: ≥290 in women; ≥305 in men
344	■ Heidelberg Spectralis: ≥305 in women; ≥320 in men
345	At least three intravitreal anti-VEGF injections given within the prior 20 weeks
346	> No previous history of glaucoma or steroid intraocular pressure response in either
347	eye
348	
349	C. Run-In Phase
350	All potential study participants will be required to participate in a 12-week run-in phase. In order
351	to enter the run-in phase, all eligibility criteria must be assessed and met. During the run-in phase,
352	study eyes will receive 3 study ranibizumab 0.3mg injections approximately 4 weeks apart.
353	
354	At the end of the run-in phase (12-week visit), eyes with persistent DME despite prior intravitreal

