405		• Visual acuity area under the curve (AUC) between randomization and 24 weeks
406		 Mean change in OCT CSF thickness, adjusted for thickness at time of
407		randomization
408		• Percent of eyes with ≥ 1 and ≥ 2 logOCT step gain or loss in CSF thickness
409		• Percent of eyes with OCT CSF thickness (in micros) < the following gender and
410		OCT machine-specific values: <290 in women and <305 in men in Zeiss Cirrus;
411		<305 in women and <320 in men in Heidelberg Spectralis
412		 OCT CSF thickness AUC between randomization and 24 weeks
413		• Percent of eyes with worsening or improvement of diabetic retinopathy on clinical
414		exam
415		
416	I.	Main Safety Outcomes
417		Injected-related: endophthalmitis, retinal detachment, retinal tears, intraocular hemorrhage,
418		increased intraocular pressure
419		1
		Ocular drug-related: inflammation, increased intraocular pressure, need for ocular anti-
420		hypertensive, glaucoma surgery, or other IOP-lowering procedures, development or
421		worsening of cataract and cataract extraction, intraocular hemorrhage, migration of
422		dexamethasone to the anterior chamber and subsequent corneal complications
423		Systemic drug-related: Deaths, participants with at least one hospitialization, participants
424		with at least one SAE, and cardiovascular events, and cerebrovascular events as defined by
425		Antiplatelet Trialists' Collaboration

426

427 J. Schedule of Study Visits and Examination Procedures

428

Visit	Enroll in Run-In	Run-In Visits*	Randomization 0	4w-24w**
Visit Window		(+/- 1w)		(+/- 1w)
E-ETDRS best corrected visual acuity ^a	Х	Х	Х	Х
OCT ^b	Х	Х	Х	Х
Eye exam ^c	Х	Х	Х	Х
Blood pressure	Х		Х	
HbA1c ^d			Х	

* Visits at 4 and 8 (\pm 1) weeks during the run-in phase. Randomization visit (0) occurs at 12 (\pm 1) weeks from enrollment.

**Visits every 4 (±1) weeks post-randomization.

a= both eyes at each visit; includes protocol refraction in study eye at each visit and the non-study eye at the randomization visit and 24 week visit. E-ETDRS refers to electronic ETDRS testing using the Electronic Visual Acuity Tester that has been validated against 4-meter chart ETDRS testing.

b=study eye

c=both eyes at enrollment and randomization and study eye only at each follow-up visit. Includes slit lamp exam (including assessment of lens), measurement of intraocular pressure, and dilated ophthalmoscopy.

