
1338

1339 7.4.1 Secondary Outcomes Analysis

1340 Analyses of secondary outcomes will be conducted as follows:

1341 Binary outcomes will be analyzed using logistic regression to control for baseline level of the

1342 outcome. Continuous outcome comparisons will be performed using ANCOVA with adjustment

1343 for baseline values. All linear model assumptions will be verified including linearity, normality

- 1344 of residuals, and homoscedasticity. If model assumptions are not met, a nonparametric analogue
- 1345 for ANCOVA will be considered. Multple imputation method will be implemented for missing 1346 data. GEE will be used to adjust for correlation between eyes of participants with two study
- 1347 eyes.
- 1348
- 1349

1350 7.5 Safety Analysis Plan

1351 Adverse events will be categorized as study eye, non-study eye, and systemic. The events will be tabulated and compared between treatment groups. Separate analyses will compare related adverse 1352

- 1353 events between groups.
- 1354
- 1355 Specific adverse events of interest will include:
- 1356 Injected-related: increased intraocular pressure, endophthalmitis, retinal detachment, retinal tears, intraocular hemorrhage 1357
- Ocular drug-related: increased intraocular pressure, need for ocular anti-hypertensives, 1358
- 1359 glaucoma surgery or other IOP-lowering procedures, development or worsening of cataract 1360 and cataract extraction, intraocular hemorrhage, inflammation, migration of Ozurdex to the anterior chamber and subsequent corneal complications 1361

1362 Systemic drug-related: Deaths, participants with at least one hospitialization, participants

with at least one SAE, and cardiovascular events and cerebrovascular events as defined by 1363 Antiplatelet Trialists' Collaboration 1364

1365 1366 • Systemic adverse events for participants with two study eves will be evaluated separately from participants with one study eye.

- 1367
- 1368

1369 Further definitions of the events for analysis and the analytic approach will be provided in the 1370 detailed statistical analysis plan.

1371 1372

1373 7.6 Additional Analysis Objectives Related to Design of Phase III Trial

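### The ocular safety table (eTable 5) counts cataract extractions but not new or worsening cataract, which protocol 7.5 names as an event of interest to be compared between groups

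*SAP*

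**What the plan says.** Protocol 1.3-I lists the main safety outcomes. Its ocular drug-related group includes the development of cataract and, in the words that follow, "worsening of cataract and cataract extraction, intraocular hemorrhage, migration of" the dexamethasone implant. Protocol 7.5 repeats the event among the specific adverse events of interest: "glaucoma surgery or other IOP-lowering procedures, development or worsening of cataract", with extraction named next. The same section says events will be "tabulated and compared between treatment groups". It then defers detail: "Further definitions of the events for analysis and the analytic approach will be provided in the" detailed statistical analysis plan.

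The SAP supplied is the technical plan for the primary manuscript. Item 6.a gives the eTable 5 rows: any ocular adverse event, raised intraocular pressure (composite and components), endophthalmitis, inflammation, retinal detachment (composite and components), retinal tears, retinal hemorrhage, vitreous hemorrhage, "Cataract extractions", glaucoma surgery, post-injection treatment to lower pressure, and implant migration. Item 6.a.ii then says "Compare the frequency between treatment groups using" Fisher's exact test.

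**The concern.** The protocol treats new or worsening cataract and cataract extraction as two events. The table carries only the second, and the two are not interchangeable. Extraction is a surgical decision, and study-eye exclusion criterion p removes eyes expected to need it during follow-up. A low extraction count over 24 weeks would therefore say little about cataract formation.

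Protocol objective (4) is "and (4) to assess the safety of administering combination steroid+anti-VEGF therapy in eyes" with persistent DME, and the trial is also meant to inform a phase III design. Protocol 1.1.5 associates cataract development with corticosteroid use, and 6.5.1.2 cites a large excess with the same implant in another disease. If eTable 5 is produced as written, readers and phase III planners will not see the between-group count for a harm the protocol itself names. Trial monitoring is not at issue: under protocol 7.8 the DSMC reviews compiled ocular events whatever eTable 5 contains. The gap is in reporting.

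**Working it through.** **1. Protocol 7.5 ocular events against eTable 5 rows**

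| Event named in protocol 7.5 | Row in eTable 5 |
|---|---|
| Increased intraocular pressure | Yes, composite and components |
| Need for ocular anti-hypertensives | Yes |
| Glaucoma surgery | Yes |
| Other pressure-lowering procedures | In part (post-injection treatment) |
| Endophthalmitis, retinal detachment, retinal tears, inflammation | Yes |
| Intraocular hemorrhage | In part (retinal, vitreous) |
| Implant migration | Yes |
| Cataract extraction | Yes |
| **Cataract development or worsening** | **None** |

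The row list runs without a break, so redaction or text extraction does not explain the gap. For implant migration, which protocol 6.5.1.2 calls rare, the plan goes further than a row. It notes "There is no specific MedDRA term for this type of adverse event" and prescribes a keyword search of the report forms.

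**2. Could another planned item supply the count?**

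- The any-ocular-event row would include a reported cataract, but pooled with effects that protocol 6.5.2 describes as common after injection, such as subconjunctival hemorrhage and floaters.
- The lens-status review in SAP 4.a.ii covers only eyes whose acuity improved or worsened and is meant for Discussion text.
- The lens-status subgroups in SAP 4.b.ii and 5.b.ii use baseline lens status to examine acuity and OCT effects. They do not count events.
- eTable 7 falls under systemic events and counts participants by system organ class.

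None of these gives eyes with new or worsening cataract by group.

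**3. How many eyes might the missing row hold?**

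The plan states no figure to reproduce, so this is an illustration.

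Inputs from protocol 6.5.1.2: cataract progression in 29.8% of phakic eyes given two implants and 5.7% of sham-treated phakic eyes, over 12 months in retinal vein occlusion. Protocol 7.1 gives 75 eyes per group.

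Assumptions: 30, 45 or 60 phakic eyes per group, and the full, half or quarter cited rates. Follow-up here is 24 weeks, and a second implant comes at week 12 or later and only if retreatment criteria are met, so the full rates are probably an upper bound. Eyes are treated as independent.

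Expected events = n × rate. For example, at full rates with n = 60: 60 × 0.298 = 17.9 and 60 × 0.057 = 3.4. Power is for the exact two-sided Fisher test at 0.05.

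| Rates | n per group | Combination | Ranibizumab | Total | Fisher power |
|---|---|---|---|---|---|
| Full | 30 | 8.9 | 1.7 | 10.7 | 58% |
| Full | 45 | 13.4 | 2.6 | 16.0 | 82% |
| Full | 60 | 17.9 | 3.4 | 21.3 | 93% |
| Half | 30 | 4.5 | 0.9 | 5.3 | 15% |
| Half | 45 | 6.7 | 1.3 | 8.0 | 37% |
| Half | 60 | 8.9 | 1.7 | 10.7 | 53% |
| Quarter | 30 | 2.2 | 0.4 | 2.7 | 1% |
| Quarter | 45 | 3.4 | 0.6 | 4.0 | 7% |
| Quarter | 60 | 4.5 | 0.9 | 5.3 | 15% |

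**4. What precision would the counts carry?**

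Newcombe 95% intervals for the difference, 45 phakic eyes per group:

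- 13 versus 3 events: 22.2 points (6.4 to 37.3), Fisher P = 0.011.
- 7 versus 1: 13.3 points (1.2 to 26.7), Fisher P = 0.058.
- 3 versus 1: 4.4 points (−5.9 to 15.8), Fisher P = 0.62.

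In the middle case the interval excludes zero while the Fisher test, which is the planned one, just misses 0.05.

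**5. For scale**

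The migration row, at the cited 2 of 342 eyes, would expect 2/342 × 75 = 0.4 events in the combination group. Every scenario in the table expects more combination-group cataract events than that.

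**The case against.** The strongest objection is that the governing document is missing. Protocol 7.5 leaves event definitions and analytic approach to the detailed SAP, and the technical plan cites version 2 of that SAP, which was not supplied. Version 2 may define the cataract outcome, tabulate it elsewhere, or explain its omission. This limits the claim to eTable 5. It does not remove it, because 7.5 defers how events are defined and analysed and does not say that a named event may be dropped.

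A second objection is that 7.5 never promises one row per event in the primary manuscript, and that the plan is selective in other ways: section 6 schedules neither non-study-eye events nor the separate analysis of related events. That is fair as a description of scope. But nearly every other ocular event in the 7.5 list did get a row, so the gap does not look like a general decision to abbreviate.

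Third, the supplied documents give no grading scale or threshold for cataract worsening, and investigators are not masked. Extraction is a cleaner event. This stands as a limit on how the counts can be read, though lack of masking also affects other investigator-reported rows that the plan keeps.

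Finally, the size rests on assumptions. With 22 phakic eyes per group and quarter rates, the expected counts fall to 1.6 versus 0.3. With all 75 eyes phakic and full rates they reach 22.4 versus 4.3. The range of 3 to 21 is therefore not a firm bound.

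**Conclusion.** The concern holds. As written, the technical plan leaves out of its between-group safety table an event that the protocol names twice and commits to comparing, and no other planned output supplies it. The omission itself is read directly from the text and needs no assumption.

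Its size is uncertain. On 30 to 60 phakic eyes per group and a quarter to all of the cited rates, roughly 3 to 21 eyes with this event would not be visible separately. At the low end a test would be nearly powerless, so the loss is mainly one of description. The correction should be made, but it is confined to reporting: efficacy conclusions and DSMC oversight are unaffected. Version 2 of the protocol SAP could change how the event is defined, but on the wording of 7.5 it would not remove the need to report it.

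**What to change.** Add one row to eTable 5 for development or worsening of cataract in the study eye, taken from MedDRA-coded adverse event reports after randomization, with number and percentage of eyes by group and the same Fisher test as the other rows. If version 2 of the protocol SAP defines the event, use that definition. If it does not, fix the list of MedDRA terms before counting by group, and state that this was done after the 21 September 2017 data set was created.

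It would also help, though the protocol does not require it, to show the number of eyes phakic at randomization in each group, since the protocol's own cited rates are per phakic eye. A footnote should say that reporting investigators were not masked and that a non-significant result on few events is not evidence of no harm.

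The cost is small. Adverse events are already MedDRA-coded (protocol 6.2), lens assessment is part of each protocol visit (4.7), and lens status is already a subgroup variable. The event was named in protocol V5.0, dated 11-16-15, so the row adds no new outcome. The remaining weakness, unmasked reporting without a stated grading threshold, is one the row can disclose but not cure.
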